**Principal Investigator – [name]**

### **1. PURPOSE OF STUDY**

We hypothesize that daily intake of sulforaphane from broccoli extract in the form of Avmacol Extra Strength (ES) can decrease kidney disease progression rate and decrease markers of oxidative stress and inflammation in Chronic Kidney Disease (CKD) patients. We will test our hypothesis in a randomized, double-blind, placebo-controlled Phase 2 clinical trial. This proposed study has been funded by National Institute of Diabetes and Digestive and Kidney Diseases (NIDDK), R01 DK128677.

We will test the safety and efficacy of Avmacol ES in CKD patients. After having established a safe dose of 4 tablets taken together daily in CKD Stages 3 – 4 in our pharmacokinetic (PK) phase (IRB protocol study 6759), we will enroll 88 patients from the Kidney Clinic in AC3, Highland Hospital, Brockport, St. James, and FF Thompson who have CKD stages 3-4 who will be randomized to Avmacol ES or placebo in a 1:1 ratio in a double-blind manner. There is a deadline for enrolling until Nov. 15, 2024, and completing study procedures by April 30, 2025, as the PI is transferring to University of California, Irvine (UCI).

### **2. BACKGROUND AND RATIONALE**

In the United States (U.S.), the prevalence of CKD in adults is ~14%. The mainstay of therapy for CKD are angiotensin-converting enzyme inhibitors (ACE-Is) or angiotensin receptor blockers (ARBs), but many CKD patients still progress to End Stages Kidney Disease (ESKD) – the ultimate in failed prevention. The prevalence of ESKD is ~ 700,000, and is projected to increase to between 971,000 – 1,259,000 patients by 2030^1.

Increased oxidative stress is a major molecular underpinning of CKD progression. In humans, a common deletion variant of the glutathione-S-transferase  $\mu$ -1 (*GSTM1*) gene, the *GSTM1* null allele (*GSTM1(0)*), results in decreased *GSTM1* enzymatic activity and is associated with higher levels of oxidative stress. *GSTM1* belongs to the superfamily of GSTs that are phase II antioxidant enzymes and are regulated by nuclear factor erythroid 2-related factor 2 (Nrf2). Our laboratory made the discovery that the highly prevalent *GSTM1(0)* is associated with more rapid CKD progression in the African American Study of Kidney Disease (AASK) trial participants. This association has been replicated in the Atherosclerosis Risk in Communities (ARIC) study and multiple other studies. In experimental mouse models of CKD or hypertension, we found *Gstm1* knockout (KO) mice have increased renal oxidative stress, inflammation, and kidney injury, compared to wild-type (WT) littermate controls.

Cruciferous vegetables in general, and broccoli in particular, are rich in glucoraphanin, a precursor of sulforaphane (SFN) that has been shown to have protective effects against oxidative damage through activation of Nrf2. We found that dietary supplementation of sulforaphane-rich broccoli powder ameliorated kidney disease only in *Gstm1* KO mice. Similarly, in the ARIC study of nearly 11,000 patients, high intake of cruciferous vegetables was associated with lower risks of kidney failure, with stronger effects in those homozygous for the null allele (*GSTM1(0/0)*). Our published paper reporting these findings was selected for news release based on “its overall excellence in furthering the field of nephrology”, and was highlighted in several news outlets, including Science Daily and Reuters Health.

SFN is currently in clinical trials for cancer of the breast, lung, and prostate, as well as autism and schizophrenia (Clinicaltrials.gov). However, very few studies have assessed the effect of SFN in kidney

disease in pre-clinical experimental models; and, to the best of our knowledge, no clinical study has been performed to assess the primary outcomes of SFN in CKD that we have included in our study. Our overarching objective is to test the safety, feasibility and efficacy of SFN in delaying CKD progression, and, if so, whether its effect is dependent on *GSTM1* genotype.

Positive results in our study will also reinforce and establish further mechanistic evidence for future research on the effects of regulation of the Nrf2-GSTM1 pathway on kidney function.

Our pharmacokinetic (PK) study showed that results from a dose of Avmacol ES 2 tablets daily were highly variable and did not achieve sufficient plasma level of sulforaphane consistently. The 6 tablets daily dose was discontinued early in the study, after consultation with the Data Safety Monitoring Committee (DSMB), due to undesirable PK profile and significant gastrointestinal side effects, raising concerns for safety and tolerability if taken for a long duration. Given the favorable side effect profile of 4 tablets daily, and the more consistent result of PK profile that is similar to published studies, we have chosen 4 tablets daily for the randomized phase of our study.

### 3. ADMINISTRATIVE ORGANIZATION

This is a multi-site collaborative study funded by the National Institutes of Health (NIH). The Nephrology Division at Strong Memorial Hospital (SMH) will conduct the study to enroll patients. Subjects will be recruited from the Kidney Clinic in AC-3, located at SMH, Highland Hospital, Brockport, St. James, and FF Thompson. The University of Virginia (UVA) will serve as a data analysis participating site (see Section #17). URMIC will securely transfer de-identified data to UVA for analysis and shared via REDCap.

### 4. STUDY DESIGN

#### **Aim 1. To test whether Avmacol ES will be safe and well tolerated in CKD patients.**

In the PK phase (IRB protocol study 6759), we established that 4 tablets of Avmacol ES is an appropriate and tolerable dose for CKD Stages 3-4 patients. We will enroll 88 patients from the Kidney Clinic in AC3, Highland Hospital, Brockport, St. James, and FF Thompson who have CKD stages 3-4 and a steady decline in estimated glomerular filtration rate (eGFR)  $\geq 3$  mL/min/m^2/year in the previous 12 months despite receiving standard of care. Patients will be randomized in a 1:1 Avmacol ES:placebo ratio. They will be given oral Avmacol or placebo for 6 months. Any side effects or adverse effects will be documented, and compliance to the study treatment will be monitored by tablet count at study visits. A comprehensive metabolic panel will be obtained as part of standard of care at each visit to monitor for any potential metabolic, renal or liver toxicity. The effect of *GSTM1* genotype on tolerability of Avmacol ES will be determined.

#### **Aim 2. To test whether Avmacol ES will improve clinical and biochemical parameters.**

At the baseline visit (month 0) and each subsequent clinic visits (typically 3 - 4 month intervals, blood pressure will be recorded, and a comprehensive metabolic profile, and urinary albumin and protein/creatinine ratio will be obtained as standard of care for patients with CKD Stages 3-4. In addition, at the baseline visit, the 1st month visit, and the two subsequent visits (3-4 months intervals), research lab work including markers of oxidative stress and inflammation, and podocyte damage (plasma and urine 8-isoprostane and plasma interleukin-6, and urine nephrin respectively), will also be assessed and compared between groups and to baseline within groups. Peripheral blood mononuclear cells (PBMCs) will also be obtained for analysis of mRNA levels of cytoprotective enzymes. This pilot study will allow us to begin to explore the effect of Avmacol ES on biomarkers of oxidative stress and inflammation. We will also explore the effect of Avmacol on the rate of decline of eGFR and compare between groups, and to the previous 6 months within group. The effect of *GSTM1* genotype on clinical and biochemical response will also be

assessed.

#### 4.1 SUBJECT POPULATION

We will enroll 88 adult patients followed in the Kidney Clinic in AC-3, Highland Hospital, Brockport, St. James, and FF Thompson with chronic kidney disease. Evaluable subjects who withdraw from the study will be replaced by subjects with CKD stage 3 or 4 to meet the enrollment goal. We will recruit patients of any gender, race, and socioeconomic status.

Enrollment will conclude by November 15, 2024 to complete subjects' 6-month timeline by April 30, 2025. At that point the PI is transferring out of URM.

**Vulnerable Subjects:** We do not plan to include vulnerable subjects such as children, pregnant women, fetuses, decisional impaired adults, or prisoners. Employees (physicians/fellows) will be assured that taking part in research is not a part of their duties, and refusing to participate in the study will not affect their job. To ensure their autonomy, the research coordinators or the PI who is not the patient's nephrologist will consent them.

#### 4.2 STUDY INTERVENTIONS

Study Drug: Avmacol Extra Strength (ES) tablets

IND # 158689

IND Holder: [name]

The study will be registered on ClinicalTrials.gov. For this double-blind and randomized, placebo-controlled trial, approximately half of the subjects will be randomized to either 4 tablets of Avmacol ES, or 4 tablets of placebo daily for 6 months. To adjust to the supplements, subjects will start the study at a dose of 2 tablets once daily for a week and then 4 tablets once daily after that for a total study period of 6 months. Nutramax will provide the tablets of both active supplement and matched placebo in bottles shipped directly to URM Clinical Research Pharmacy Investigational Drug Services (IDS) to store, monitor, and dispense.

If the subjects experience side effects at a dose of 4 tablets together daily, they will be asked to stop taking the supplements for a week and resume at a dose of 3 tablets together daily. If they experience side effects at this dose, this will be asked to stop taking the supplements for a week again and resume at a dose of 2 tablets together daily. If they still experience side effects, they will be withdrawn from the study for safety. In case of a health emergency, the subject's healthcare provider and/or nephrologist will be unblinded to the study treatment (supplement versus placebo) by paging the IDS office.

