## 9. RISKS TO SUBJECTS

### Sulforaphane/Avmacol ES (Study Drug)

There are some potential risks to participants since we are introducing a well-tolerated study drug in other clinical trials but has not been previously tested in CKD patients. We take careful precautions by first establishing an optimal dose of Avmacol ES in CKD patients using reported peak plasma concentrations in trials that were conducted in patients without kidney disease. Based on the multiple clinical trials that have been done with Avmacol or the actual sulforaphane compound in other diseases, we do not anticipate any serious risks. The most common side effects are gastrointestinal, including nausea and dyspepsia, which are ameliorated when taken after a meal.

Although not reported in any earlier trial nor in our PK phase of the study, there is the possibility of an allergic reaction to the study drug. This reaction may be mild, such as a skin rash, or more severe symptoms like swelling of the throat, low blood pressure, and shortness of breath. In rare cases, a severe reaction could cause death.

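### The dose step-down rule in Section 4.2 is not limited to tolerability effects, so a non-emergency suspected allergic reaction would, read literally, be handled by restarting the tablets

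*Combined protocol and SAP*

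**What the plan says.** Section 4.2 sets the dosing: "subjects will start the study at a dose of 2 tablets once daily for a week and then 4 tablets once daily after that". It then gives one rule for trouble. The trigger is "If the subjects experience side effects at a dose of 4 tablets together daily", and the action is that "they will be asked to stop taking the supplements for a week and resume at a dose of 3 tablets together daily". If side effects return at 3 tablets there is a second week off and a restart at 2. If they persist at 2 tablets the subject is withdrawn. No type, severity or suspected mechanism is specified. A separate sentence, opening "In case of a health emergency", provides for unblinding the treating clinician; it does not mention stopping the tablets.

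Section 13 makes side effects a reason for withdrawal when reducing the dose has not resolved them. It lists no criterion for allergy.

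Section 9 describes what is expected of the study drug: "The most common side effects are gastrointestinal, including nausea and dyspepsia". A separate paragraph says that an allergic reaction is possible, although none was reported in earlier trials or in the PK phase. Of that reaction it says "This reaction may be mild, such as a skin rash, or more severe symptoms like swelling of the throat", and then "In rare cases, a severe reaction could cause death". It gives no instruction on what to do with the tablets.

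**The concern.** For a dose-related effect such as nausea, a pause and a restart at a lower dose is sensible. For a suspected allergic reaction it is the wrong response, because the restart re-exposes the subject to the suspected cause. The protocol names both kinds of effect as risks of the drug but writes one management sequence, and its trigger does not separate them.

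The practical case is a rash or similar reaction that nobody treats as an emergency. A coordinator who follows Section 4.2 as written would tell that subject to pause for a week and restart at 3 tablets.

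**Working it through.** The point concerns the wording of a rule, so the check sets the relevant sections side by side. The only arithmetic is the cost of the fix.

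**1. Is the trigger limited anywhere in the visible text?**
- Section 4.2: no limit by type, grade or causality.
- Section 2: the 6-tablet dose was dropped "due to undesirable PK profile and significant gastrointestinal side effects". This suggests that tolerability was in mind, but it explains the choice of dose and does not define the step-down trigger.
- Section 9: gastrointestinal effects are called the most common side effects. Most common does not mean only.
- Section 13: repeats the dose-reduction logic without narrowing it.

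**2. Does another provision keep a subject with a suspected allergic reaction off the tablets?**
- Symptom call at about 2 weeks (Section 8, Study visits): new symptoms are assessed to see whether more evaluation is needed. No stopping instruction is attached.
- Emergency sentence (Section 4.2): unblinding only.
- DSMB text ahead of Section 18: a serious adverse event leads to a meeting on whether to suspend the study. That concerns the trial rather than one subject's dosing, and a non-serious rash would not trigger it.
- Pregnancy (Section 9): an explicit instruction to stop at once on suspicion. So the protocol writes such an instruction where one is wanted, but the visible text has none for suspected allergy.

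**3. What does the literal sequence do?** It allows up to two restarts, at 3/4 = 75% and then 2/4 = 50% of the full daily count, each after one week off. These figures describe exposure and do not measure harm. The documents give no rate for allergic reactions, so no number of affected subjects can be estimated.

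**4. What would stopping cost the primary comparison?** Inputs from Section 18: 44 per arm, placebo mean 400 pg/mL, active mean 300 pg/mL, SD 150 pg/mL, two-sided 5% error (the plan says 5% and a two-sample *t*-test; two-sided is assumed). Section 18 states no power percentage, so there is no figure of the plan's own to reproduce.

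Normal approximation: power = Φ(Δ/SE − 1.96), with SE = 150 × √(2/44) = 31.98.

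Assume that *k* active-arm subjects stop, stay in the analysis, lose the whole effect and are not replaced, with SD unchanged. Then Δ = 100 × (44 − *k*)/44.

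| *k* | Δ (pg/mL) | Δ/SE | Power |
|---|---|---|---|
| 0 | 100.0 | 3.127 | 87.8% |
| 1 | 97.7 | 3.056 | 86.3% |
| 2 | 95.5 | 2.985 | 84.7% |

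Each such subject costs about 1.5 points (87.8 − 86.3 = 1.5; 86.3 − 84.7 = 1.6). A placebo subject who stops does not dilute the assumed effect.

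**The case against.** The strongest reply is that context already limits the rule. It follows directly on the titration text; Section 13 speaks of effects that respond to dose; Section 2 ties the dose choice to gastrointestinal effects; and Section 9 puts allergy in its own paragraph, apart from the common side effects. This is probably what was meant, and it stands as a reading of intent. It does not close the gap: if allergy lies outside the rule, no visible rule covers it.

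The reply also points to existing review. Side effects and adverse events are assessed at about 2 weeks and at each month from 1 to 6, the DSMB sees unblinded safety data, and nothing bars the investigator from stopping a subject's tablets. That stands too, and it lowers the probability of harm, but it rests on unwritten discretion.

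The latest version date shown is 13 November 2024, two days before enrollment closes, so the period left in which the wording could matter is short.

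Three stronger readings are tempting and are not supported:
- *That the plan directs rechallenge after a severe reaction.* Throat swelling or low blood pressure would fall under the emergency sentence, and clinicians would very likely not restart. The risk of death in Section 9 belongs to severe reactions and should not be carried over to a mild rash; no section says that a mild reaction worsens on re-exposure.
- *That a subject who reacts in the 2-tablet first week is told to go up to 4.* Section 4.2 has no rule for that week, but no text orders escalation despite a reaction. That would be an inference from silence.
- *That the study has no allergy instruction at all.* Some text just before the DSMB description, and the consent pages, were not available to this review, and an instruction could sit there.

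**Conclusion.** The concern holds as a low-probability safety wording defect that should be corrected. The unqualified trigger, followed literally, brings a subject with a non-emergency suspected drug rash back onto the tablets up to twice before withdrawal, and no visible text exempts that case. It goes beyond missing detail because the rule that is written gives the wrong action for a risk that the protocol itself names.

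The size of the harm cannot be put in numbers. The conclusion rests on the visible text alone and on the assumption that a rash might be handled as an ordinary side effect.

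**What to change.** In Section 4.2:
- Limit the step-down to tolerability effects, for example gastrointestinal ones.
- State that for a suspected allergic reaction at any dose, including the 2-tablet first week, the tablets are stopped pending investigator assessment and are not restarted unless the investigator documents a clear alternative cause.
- Apply this identically in both arms, without unblinding.
- State that such a subject stops tablets but not the study: with the subject's agreement the remaining month 1, 3 and 6 visits are kept, the subject stays in the randomised arm, and is not replaced as a dropout. This needs saying because Sections 13 and 18 replace dropouts. For the same reason, allergy should not be added to Section 13 as a reason for leaving the study.

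The cost is a few sentences, a short notice to staff and a routine IRB modification, with no extra visits or staff. The downside is that an unrelated rash may occasionally end a subject's treatment, at the power cost worked out above. The documented-alternative-cause clause keeps that number down, and up to three post-baseline samples per such subject are retained.

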### 5. INCLUSION AND EXCLUSION CRITERIA

#### **Inclusion Criteria:**

- Age  $\geq 18$  years and  $\leq 80$  years
- Estimated glomerular filtration rate (eGFR)  $\geq 20$  and  $< 60$  mL/min/1.73m^2 and a decline in eGFR of  $\geq 3$  mL/min/1.73m^2/year in the previous 12  $\pm$  2 months
- Able to provide consent
- Able to swallow Avmacol ES or placebo tablets

#### **Exclusion Criteria:**

- Significant co-morbid conditions with life expectancy of  $< 1$  year
- Serum potassium of  $> 5.5$  mEq/L at screening
- New York Heart Association Class 3 or 4 heart failure symptoms, known Ejection Fraction (EF)  $\leq$

- 30% or hospital admission for heart failure within the past 3 months
- Factors judged to limit adherence to interventions based on appointment attendance and medication treatment compliance; PI will make this determination.
- Current participation in another medical intervention study
- Known to be pregnant or planning to become pregnant or currently breastfeeding; determined by self-report and medical record history. Before dispensing the study supplements at the baseline visit, and repeated thereafter at every study visit (~month 1 and ~ every 3-4 months thereafter), a urine pregnancy test will be completed for individuals of child bearing potential, unless they have had a hysterectomy, or they are over 50 years of age and their last menstrual cycle was over two years ago.
- Cognitive impairment as determined by the patient's provider. The study coordinators will send an in-basket message to the patient's provider to determine whether they are able to provide informed consent. This will also be assessed if the patients are approached in-person after their kidney clinic appointment. Lastly, as is done for all study participants, comprehension will be tested at the time of obtaining informed consent by asking key questions about the study.
- On anticoagulants or immunosuppression
- Under treatment for cancer
- Delayed gastric emptying or similar GI conditions

Non-English-speaking individuals are excluded in this randomized phase of the study because the lack of English proficiency will affect a subject's ability to report problems or adverse events. If a patient cannot read, the consent form will be read to them by the research coordinator.

## 6. RECRUITMENT METHODS

Once eligible patients are identified, our research coordinator will reach out to each provider to ask if they would like to introduce the study to the patient and whether we may speak with their patients about the details of the study.

**Phone/Video Call:** The research coordinator will contact eligible patients by phone to introduce the study and gauge interest. IRB approved phone scripts will be used for calls.

- If the patient is interested in participating, a follow-up phone or Zoom video call will be scheduled with the patient 7 to 10 days after the initial call and recruitment email is sent.
- On the call or after obtaining informed consent, the patient will be asked for preferred method of communication: Call, Text, or Email.
- To send PDFs of the IRB approved consent form and recruitment material via email for their review, the study team member will obtain their permission to use email, per the following: *"Because URMIC can't control the security of email messages once we send them, we need your permission to email you. Do you want to receive the link to the consent via email?"*.
- While the subject is on the phone, our research coordinator will provide the option of reviewing the consent form either by phone or via zoom. However, obtained/documented consent will occur in person as noted in Section 7.

**Email:** One recruitment email will be sent to eligible patients after the study is introduced by phone and the patient has verbally agreed to receive recruitment email communications. If they say no, we will approach them to provide the material the next time they come to clinic for a visit.

The email will include a copy of the informed consent, a study flyer or brochure, an agreed time for a follow-up call, to occur either by phone or Zoom video, for the research coordinator to review the consent form and discuss the patient's participation further. Alternatively, this will be done at the patient's next routine health visit if it is scheduled around the time of the initial phone call.

**Texting:** Doximity, a secure texting service approved at UPMC, will be used for scheduling and appointment reminders.

**Mail:** If the study participant does not prefer email, the informed consent form can be mailed with a cover letter that will instruct the potential subject not to sign/date the consent form as a follow up phone or Zoom call will be made by the study coordinator to review with them. The consent will not be signed/returned via US postal; all consent will be obtained in person; refer to Section 7-Consent Process.

**Flyer & Brochure:** Study flyers/brochures will be displayed in Kidney Clinic in AC-3, Highland Hospital, Brockport, St. James, and FF Thompson clinic waiting area and restrooms. Subjects who contact the study team directly and leave a voice mail will receive a follow-up phone call by the study coordinator, per the phone script submitted for IRB approval. If they contact the study team via email, then they will include a copy of the informed consent, a study flyer or brochure, requesting a time for a phone or Zoom video call for the research coordinator to review the consent form and discuss the patient's participation further.

**Clinic Appointment:** During the subject's Kidney Clinic appointment at either SMH or Highland Hospital, the research coordinator may approach or follow-up with the subject to discuss the details of the study and give an opportunity to ask their Nephrologist related questions or concerns. Nephrologist may also initiate information on study participation.

For the patient's convenience, the study coordinators will try to schedule study visits on or around their routine health visits to the clinic.

**@Rochester:** Information about the study will be included in the @Rochester email newsletter.

**Clinical studies admin:** A QR code or link to a prescreening form will be added to the email sent out to participants on the UR Health registry.

**MyChart:** Potentially eligible subjects will receive an email or text notifying them that they have a new research opportunity available in MyChart. It can only be viewed after they log in to MyChart and visit the Research Studies page. Subjects will see a description of the study, which is included on the attached MyChart for Recruitment Request form (uploaded as part of recruitment materials). Underneath the study description on the Research Studies page, subjects will indicate whether or not they are interested in participating by clicking on the corresponding button. This will trigger a notification that is sent to the study coordinator's InBasket in eRecord.

Interested subjects will then be contacted as described in this protocol. Subjects who are not interested will not be contacted and will be removed from the pool of eligible subjects. If subjects do not indicate whether or not they are interested in participating, they may be re-sent the email notification one additional time, no sooner than one week after the first email was sent. When study accrual has been completed, outstanding research opportunities in MyChart will be rescinded.

The study coordinators will send a direct MyChart message about the study to eligible patients via MyChart.

